21.3.3 Medical Monitoring Review

The MM (see [Section 20.1](#)), CRA and the Sponsor should be notified about SAE by the study Investigator or his/her designee, by email or fax, as soon as possible and not later than 24 hours after the event.

The MM is responsible for initial review of these events within two (2) days of the notification. The MM review will be documented. If the MM requires additional information to make an assessment, the clinical site will have two (2) days to respond to the request. Most information should be available within four (4) days of the site's knowledge of the event.

21.3.4 Reporting to Regulatory Authorities

The Sponsor or his authorized representative will notify the FDA or any other relevant regulatory authorities of any unexpected, serious adverse event or fatal or life-threatening experience associated with study procedures as soon as

possible, in accordance with regulatory requirements. As per 21 CFR 312.32, unexpected fatal or life-threatening suspected adverse reactions are reported by telephone or fax no later than seven (7) calendar days after knowledge of the event. All serious, unexpected, suspected adverse reactions and Grade 3-4 ocular toxicities (except cataract) related to the investigational product, such as intraocular infection, inflammation, retinal detachment, tumor/ectopic tissue formation will be reported to the FDA via a written report within fifteen (15) days of receipt of the information.

21.4 FOLLOW-UP OF THE ADVERSE EVENTS

Subjects who experienced AEs will be followed until resolution or stabilization. SAEs that are ongoing at the end of the study period will be followed up to determine the final outcome. Any SAE that occurs after the study period and is considered to be possibly related to study participation will be recorded and reported immediately.

22. STATISTICAL METHODOLOGY

22.1 STUDY DESIGN AND SAMPLE SIZE

As this is an open-label, phase I/IIa dose escalation, safety, tolerability and preliminary efficacy study, neither power assessment, nor formal hypotheses testing are currently planned for study outcome measures.

Detailed methodology for data summary and analyses will be documented in a Statistical Analysis Plan (SAP). This document may modify the plans outlined in the protocol; however, any major modification of the outcome measures and/or its analysis will also be reflected in a protocol amendment. Additional statistical analyses other than those described in this section may be performed if deemed appropriate and included in the SAP.

The planned sample size of approximately 24 eyes for 4 study cohorts to be treated with targeted OpRegen® doses of 50×10^3 and up to 200×10^3 cells, is considered clinically appropriate for further characterization of the safety, tolerability and preliminary efficacy of OpRegen® in the treatment of subjects with subjects with advanced dry-form AMD with GA.

22.2 ANALYSIS SETS

22.2.1 Modified Intent-to-Treat (mITT) Analysis Set

The Modified Intent-to-Treat (mITT) analysis set will consist of all subjects who have been enrolled to the trial and received the OpRegen® implantation. This analysis set, which will include all data captured in database for these subjects, will serve as the primary Analysis Set for inference.

22.2.2 **Per Protocol (PP) Analysis Set**

The Per Protocol (PP) analysis set is a subset of the mITT Analysis Set and will consist of all subjects who have been enrolled into the trial, received the OpRegen® implantation and violated none of the major protocol guidelines.

22.3 **SIGNIFICANCE LEVEL**

No formal hypothesis testing is planned for this study. However, a significance level of 0.05 using two-tailed tests will be utilized in the case that exploratory significance testing will be performed.

22.4 **INTERIM REPORTS**

Comprehensive interim reports of accumulated safety, tolerability and preliminary available efficacy data will be presented to the independent Data Safety Monitoring Board (DSMB).

Depending on the safety data available, there will be a DSMB recommendation to pursue one of the following alternatives: proceed to the next higher dose; stop dose escalation; investigate a lower dose; or repeat a dose level.

22.5 **DESCRIPTIVE STATISTICS**

All measured variables and derived parameters will be listed individually and if appropriate, presented in summary tables by dose regimen group and overall, providing sample size, absolute and relative frequency for categorical variables, or sample size, arithmetic mean, standard deviation, median, minimum and maximum for continuous variables. Confidence intervals will be presented for the efficacy endpoints for exploratory purposes only.

22.6 **MISSING DATA**

Every effort will be made to complete follow-up for all subjects and avoid missing data, in particular regarding essential items. For other cases of missing data, the “last observed value” (LOV) approach will be used when appropriate.

22.7 **SUBJECT DISPOSITION**

Data from subjects who are screened but not treated, subjects in the mITT and PP Analysis Sets, as well as trial withdrawals from study follow-up will be summarized using descriptive statistics.

22.8 **DEMOGRAPHIC AND BASELINE CHARACTERISTICS**

Demographics, baseline data as well as disease prognostic factors, medical history, and prior medications will be summarized for the mITT analysis set using descriptive statistics.

22.9 CONCOMITANT MEDICATIONS USE

The WHO drug dictionary will be used to classify medications verbatim for Concomitant Medication and Pre-Trial Medications.

Analysis of concomitant drug use will be performed in the following manner:

- Pre-Study IP Implantation Medications Use: Analyses will include coded medications that were initiated prior to study IP implantation, regardless stopping date. An incidence table including patient counts (no. of subjects) and percentages broken down by Medication Class and Preferred Term will be provided.
- Concomitant Medications Use (Post-Study IP Implantation): Analyses will include only coded medications that were consumed following study IP implantation, regardless if drug initiation date was before or after it. An incidence table including patient counts (no. of subjects) and percentages broken down by Medication Class and Preferred Term will be generated.

22.10 EVALUATION OF SAFETY

22.10.1 Treatment Emergent Adverse Events (TEAEs)

AEs will be recorded from the time a subject has signed the Informed Consent. All AEs reported by the investigators will be coded according to the current version of the MedDRA dictionary.

The following will be incorporated into the analysis of AEs:

- All analyses to be provided will include coded AEs.
- AEs analyses will include only the TEAEs, namely, those events which started following study IP implantation. Listings of both TEAEs and non-TEAEs will be provided.
- Summary tables of TEAEs will be provided by Study Cohort and overall.
- The incidence (no. of subjects) and frequency (no. of events) of TEAEs will be provided when broken down by System Organ Class (SOC) and by Preferred Term (PT) according to MedDRA dictionary.
- Breakdowns of TEAEs by all of the AEs attributes (e.g. seriousness, severity) will also be provided.
- Breakdowns of TEAEs by age and sex will also be provided.
- The derived dictionary used in the analyses displaying the MedDRA System Organ Class (SOC), the Preferred Term (PT), and the AE Verbatim Term as specified by the Investigator, will be provided.

22.10.2 Safety Laboratory Tests

Analyses of safety laboratory data will be performed in the following manner:

- Summary tables of safety laboratory parameters will be provided by Study Cohort and overall.
- Box-Plots of laboratory measurements before study IP administration and afterwards by scheduled visit and will be provided. In this analysis baseline values are the measurements taken up study IP administration,

while “during trial” evaluations are the measurements taken after that time point.

- Descriptive statistics of quantitative tests results and changes from baseline by scheduled visit will also be provided. The analysis algorithm as described for the above Box-Plots assessments will be used for this analysis as well.
- Quantitative laboratory measurements will be categorized with reference to the normal ranges as Low, Normal, or High. Shift analysis of the categorical change from baseline to each scheduled visit and to the last observed assessment will also be performed.
- A list of parameters and related cut-off values defining the potentially clinically significant (PCS) abnormal values will be outlined by the Sponsor. Measurements used in the analysis are those taken following study IP administration. The incidence tables of PCS lab values as well as the individual patient listing will be provided using the denominator which is the number of subjects with at least one post-baseline administration of trial medication. Individual subjects’ listings of PCS measurements will also be presented.

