Cohort 4 will include two formulations; subjects will be treated with either OpRegen® BSS Plus or OpRegen® ‘Thaw-and-Inject’ (TAI) formulation, which is based on the use of CryoStor® 5, a serum-free, animal-free GMP grade cryopreservation solution. Additionally, this Cohort includes two options for subretinal delivery systems: DORC² or the Orbit SDS (an FDA 510K class II device cleared under K182274 on 20 November 2018). Please refer to the instructions for use (IFU) for each device for more information.

Staggered intervals will be applied between at least the first two subjects of each delivery modality to ensure subject safety and welfare.

[REDACTED]

[REDACTED]

All Cohorts

The study is being conducted in participants with confirmed bilateral GA (Study Eye and Non-Study, Fellow Eye).

Between cohorts and subjects, where applicable, the next step to proceed will be per Data Safety Monitoring Board (DSMB) recommendation, based on accumulated safety data.

Cell suspension will be delivered into the subretinal space in the macular area as described in the IFU and operating manuals for each delivery device.

[REDACTED]

[REDACTED]

[REDACTED]

[REDACTED]

[REDACTED]

Along with the relevant surgical procedure, subjects will receive systemic immunosuppression [REDACTED], consisting of the following:

- [REDACTED]
- Systemic (PO) tacrolimus 0.01 mg/kg daily [REDACTED] up to 6 weeks post transplantation,
- Systemic (PO) mycophenolate mofetil, up to 2 gr/day, [REDACTED] for at least three months [REDACTED] post transplantation, [REDACTED]

During Part 1 of the study, subjects will be assessed at pre-scheduled intervals throughout the [REDACTED] following the implantation of OpRegen®. Any side effects related to the immunosuppressive treatment will be monitored and followed up (e.g. improve blood pressure control if hypertension develops). In the case of uncontrollable side effects, treatment with the immunosuppressive agents described above will be modified in consultation with the Medical Monitor.

Part 2 of the study includes long term follow-up visits that will occur at [REDACTED]

Study Population and Number of Subjects

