- Reading Speed Test (for subject's proficient in English)

Final decision for subject eligibility upon confirmation of Central Reading Center and the Sponsor.

Immunosuppression therapy will be prescribed, if subject is eligible for enrollment, as detailed in [Section 9.3.1](#). [REDACTED] will be measured during the [REDACTED].

General Safety Assessment including prior and concomitant medications and adverse events will be performed during all visits.

[REDACTED]

- LOCS III (baseline 1)

[REDACTED]

11.3.1 [REDACTED]

The subjects can be hospitalized (if country specific requirement) [REDACTED] per investigator discretion. The following procedures and assessments will be performed on the [REDACTED]:

- General safety assessment (AEs and concomitant medication)
- Vital signs
- Medical History
- Physical examination
- Dilated Fundus Examination
- IOP

- Slit Lamp Exam
- SD-OCT (central reading)
- FAF (central reading)
- CFP (central reading)
- Immunosuppression assessment
- [REDACTED]
- BCVA
- Low Luminance BCVA (optional for cohort 4 subjects with low vision who are not able to perform this test and is not applicable for cohorts 1-3)
- Complete Blood count (including differential)
- Chemistry (including Serum Electrolytes)
- Coagulation – and confirmation that aspirin/aspirin containing drugs and other coagulation modifying drugs were discontinued
- Urinalysis
- Reading speed test, if not performed during Screening for subject's proficient in English
- HLA-typing will be performed during [REDACTED] or during one of the subsequent visits if not performed during [REDACTED].

[REDACTED]

[REDACTED]

The results will be reviewed by the associated principal investigator to re-confirm subject's eligibility.

[REDACTED]

[REDACTED]

The following procedures and assessments will be performed on the [REDACTED] prior to implantation:

- General safety assessment (AEs and concomitant medication)
- Vital signs
- Dilated Fundus Examination (optional)
- IOP (optional)
- Slit Lamp Exam (optional)
- [REDACTED]

[REDACTED]

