14.1.2 Assessment of Systemic Toxicity

Physical examination at regularly-scheduled time points will be performed by the clinical trial medical personnel to allow detection of and response to any acute symptoms. Complete blood count with differential, INR, PTT, serum chemistry, measures of hepatocellular integrity and renal function (including BUN and creatinine) and urinalysis will be performed during the [REDACTED], serving as a baseline, pre-implantation evaluation, and during post-treatment evaluations. These tests will allow detection of toxicity in a number of organ systems. In addition, safety information will be obtained by specific questioning. Systemic toxicity will be graded based on the scale shown in Section 21.1.7.

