#### 4.1.2 Baseline and Change from Baseline

Unless indicated otherwise, change from baseline (CFB) will be calculated as follows, where the baseline assessment is the last assessment before OpRegen injection:

$$\text{CFB} = \text{Value at Visit} - \text{Baseline}$$

Percent change from baseline (PCFB) will be calculated as follow:

$$\text{PCFB (\%)} = 100 * (\text{Value at Visit} - \text{Baseline}) / \text{Baseline}$$

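### Laboratory and vital-sign changes have a baseline anchored only at OpRegen injection; add a second reference taken before the first immunosuppressant dose

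*Protocol*

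**What the plan says.** **Baseline.** Protocol 22.10.2 (laboratory tests) states: "In this analysis baseline values are the measurements taken up study IP administration". Protocol 22.10.3 uses the same sentence for vital signs. Neither section says which measurement counts when there are several. SAP 4.1.2 does: "the baseline assessment is the last assessment before OpRegen injection". It allows for exceptions, but none for laboratory tests or vital signs is visible.

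**Use of the baseline.** The Protocol plans box-plots and changes by visit for both data types, and Low/Normal/High shift tables for laboratory data. Protocol 7.3.1 lists treatment-emergent changes in vital signs and laboratory tests among the safety endpoints.

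**Immunosuppression.** Tacrolimus runs "up to 6 weeks post transplantation" and mycophenolate for at least three months after implantation. The start of both is blacked out in the Synopsis and in Section 9.3.1. The screening-visit text says: "Immunosuppression therapy will be prescribed, if subject is eligible for enrollment". The next visit described, still before implantation, lists vital signs, blood count, chemistry, urinalysis and an immunosuppression assessment. Vital signs appear again in a list introduced by: "The following procedures and assessments will be performed on the [REDACTED] prior to implantation". Section 14.1.2 describes laboratory tests at a redacted visit as "serving as a baseline, pre-implantation evaluation, and during post-treatment evaluations". The Synopsis provides for managing side effects of the immunosuppressants, for example: "improve blood pressure control if hypertension develops".

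**SAP tables.** SAP 7.1.7 and 7.1.8 name summary statistics of laboratory and vital-sign values. They name no change from baseline and no shift table.

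**The concern.** Every subject is to receive OpRegen together with mandated systemic drugs, but the reference point for safety change is tied to OpRegen alone. If dosing begins before the last pre-injection reading, that reading may already carry part of the drugs' effect on blood pressure or laboratory values. Three things could follow:

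- The change from baseline understates the effect while the subject is on drug.
- When a reversible effect ends, the return to the subject's usual level looks like an improvement. Part 1 lasts about 52 weeks, so many visits can fall after tacrolimus has stopped.
- A subject who moves from Normal to High before implantation enters the shift table as High and shows no shift.

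With 3, 3, 6 and 12 subjects per cohort, one hidden shift can alter how a cohort's table reads.

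**Working it through.** The documents give no figure on this point, so there is nothing to reproduce. The size follows from simple algebra with one unknown.

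**1. Change from baseline.** Let V be a subject's level without drug, D the full effect on drug, and p the share of D present at the last pre-injection reading.

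- Baseline = V + pD
- Change on drug = (V + D) − (V + pD) = (1−p)D
- Change after a reversible effect has ended = V − (V + pD) = −pD
- Against a value taken before the first dose, the two changes are D and 0.

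Take D = 20% of V, an assumed value for illustration (for example, serum creatinine):

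| p | On drug, pre-injection baseline | After drug, pre-injection baseline | On drug, pre-dose reference | After drug, pre-dose reference |
|---|---|---|---|---|
| 0 | +20% | 0% | +20% | 0% |
| 0.25 | +15% | −5% | +20% | 0% |
| 0.5 | +10% | −10% | +20% | 0% |
| 1 | 0% | −20% | +20% | 0% |

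These are percentages of V. The percent change in SAP 4.1.2 divides by the raised baseline, so it differs slightly. At p = 0.5 it is 10/110 = 9.1% in each direction.

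**2. How much dosing could precede implantation.** Let d be the days of dosing before implantation, which must be assumed because the start is redacted. Take 42 days after implantation for tacrolimus (6 weeks) and 84 for mycophenolate (3 months of 28 days, the month length used in the Protocol's visit schedule). The share of dosing days before implantation is d/(d + 42) or d/(d + 84).

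| d (days) | Tacrolimus | Mycophenolate |
|---|---|---|
| 0 | 0% | 0% |
| 1 | 1/43 = 2.3% | 1/85 = 1.2% |
| 3 | 3/45 = 6.7% | 3/87 = 3.4% |
| 7 | 7/49 = 14.3% | 7/91 = 7.7% |
| 14 | 14/56 = 25.0% | 14/98 = 14.3% |

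For these values of d most dosing falls after implantation. These are shares of dosing days, not of effect, so they do not determine p.

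**3. Shift tables.** The algebra does not carry over to categories, because a 20% change need not cross a limit of normal. What can be lost is a crossing that happened before implantation: Normal, then High, then High is tabulated as High to High.

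**4. What the visible text settles.** Prescription comes before implantation, and laboratory and vital-sign readings are taken between the two. The text does not show when the first dose is taken, which visit Section 14.1.2 calls baseline, or on which day the final vital signs are read. So p stays between 0 and 1.

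**The case against.** The strongest reply is that the deciding fact is not visible. Prescribed does not mean taken. Protocol 19.5 gives the immunosuppression assessment two purposes, and the first is to judge whether the subject is fit for the drugs, so an assessment before surgery is compatible with no dose yet. The Protocol does not pick one pre-implantation measurement; only the SAP does. All of this stands, and it is why the finding is conditional.

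Harm also has other routes into the report:

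- The analysis of potentially clinically significant values applies cut-offs to post-implantation measurements, with no baseline subtraction described.
- Individual values are listed.
- Clinically significant laboratory abnormalities become adverse events.
- SAP Table 14.3.1.4.2 breaks treatment-emergent events down by relationship to per-protocol treatment.
- Pre-implantation results are reviewed to re-confirm eligibility, so a marked abnormality should be noticed.

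This stands for harm arising after implantation. It is less complete for the window before it: Protocol 22.10.1 keeps events that start before implantation out of the adverse-event tables and in listings only, and SAP 7.1.6 brings them back only if they worsen afterwards.

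Finally, the primary objective is the safety of OpRegen, so a baseline at injection is a defensible choice. That argues against replacing it, but not against a second reference beside it.

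**Conclusion.** The point holds conditionally. If immunosuppressant dosing starts before the last pre-injection reading, the Protocol's change summaries show (1−p) of the effect on drug and −p of it after a reversible effect ends, and shift tables may miss category changes that occurred before implantation. If dosing starts at or after that reading, p = 0 and nothing is lost. The algebra assumes that the full effect D is reached on drug and is reversible.

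Two stronger readings are tempting and are not supported:

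- A reader might infer that harm from the immunosuppressants is subtracted out of the safety results. That would need p = 1, which no visible text shows, and harm arising after implantation remains visible in any case.
- A reader might infer that the vital-sign baseline is distorted by stress on the day of surgery. The day is redacted, and neither document mentions such an effect.

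The mechanism belongs to the Protocol's planned summaries. SAP 7.1.7 and 7.1.8 name no change from baseline, which is itself a mismatch to resolve. Nothing here is a comment on the immunosuppression regimen.

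**What to change.** 1. In Protocol 22.10.2 and 22.10.3, state that the baseline for change after implantation is the last pre-injection value, as SAP 4.1.2 already has it.
2. In those sections and in SAP 4.1.2, add a second reference for laboratory tests and vital signs: the last value before the first dose of any per-protocol immunosuppressant. For laboratory tests this is the screening value. For vital signs it is the last available pre-dose reading, because screening vital signs are not visible in the text.
3. Present the Protocol's change and shift summaries against both references.
4. Align SAP 7.1.7 and 7.1.8 with Protocol 22.10.2 and 22.10.3.
5. Leave the ocular baselines unchanged.

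The cost is the wording, one derived variable and one extra column. Laboratory values should already exist, because eligibility depends on blood and urine results. If dosing turns out to start at implantation, the added reference does no harm.

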22.10.3 Vital Signs

Analyses of vital signs (blood pressure, pulse, temperature, and respiration rate) will be performed in the following manner:

- Summary tables of vital signs will be provided by Study Cohort and overall.
- Box-Plots of vital signs before study IP administration and afterwards by scheduled visit and will be provided. In this analysis baseline values are the measurements taken up study IP administration, while “during trial” evaluations are the measurements taken after that time point.
- Descriptive statistics of quantitative tests results and changes from baseline by scheduled visit will also be provided. The analysis algorithm as described for the above Box-Plots assessments will be used for this analysis as well.
- A list of parameters and related cut-off values defining the potentially clinically significant (PCS) abnormal values will be outlined by the Sponsor. Measurements used in the analysis are those taken following study IP administration. The incidence tables of PCS lab values as well as the individual patient listing will be provided using the denominator which is the number of subjects with at least one post-baseline administration of trial medication. Individual subjects’ listings of PCS measurements will also be presented.

